This study will include adults and children (≥ 6 years of age) with a documented diagnosis of PH1 based on urinary oxalate excretion ≥ 0.70 mmol/24h/1.73m² and confirmed alanine glyoxylate aminotransferase (*AGXT*) mutations, and eGFR ≥ 30 mL/min/1.73m² at screening.

Study Drug, Dose, and Mode of Administration

Lumasiran (ALN-GO1) is an investigational agent comprised of a synthetic, small interfering RNA (siRNA) (drug substance ALN-65585) covalently linked to a triantennary N-acetylgalactosamine (GalNAc) ligand, designed to target liver *hydroxyacid oxidase 1 (HAO1)* mRNA, blocking production of glycolate oxidase (GO) and hence reducing hepatic oxalate production.

Lumasiran will be administered at a dose of 3.0 mg/kg as a subcutaneous (SC) injection. See [Figure 1](#) for the dose schedule.

Reference Treatment, Dose, and Mode of Administration

[figure not shown]
The control drug for this study will be a placebo (sodium chloride 0.9% w/v for SC administration). See [Figure 1](#) for the dose schedule.

Duration of Treatment and Study

The duration of treatment with study drug is up to 5 years, including a 6-month double-blind treatment period followed by a 3-month blinded treatment extension period, and up to a 51-month open-label extension period.

The estimated total time on study, inclusive of screening, for each patient is up to 62 months, including up to 2 months of screening followed by up to 60 months of treatment.

Figure 1: Study Design

Abbreviations: q3M=once every 3 months; qM=once monthly; qMx3=once monthly for 3 consecutive months

* Patients randomized to lumasiran will also receive 2 qM doses of placebo during the 3-month blinded treatment extension period.

Table 1: Schedule of Assessments – 6-Month Double-Blind Treatment Period and Blinded Treatment Extension (Screening through Month 9 Assessments)

Study Visit	Note	Screening	6-Month Double-Blind Treatment Period								3-Month Blinded Treatment Extension Period		
			Base line	Wk 2	M1	M2	M3	M4	M5	M6	M7	M8	M9
Study Day (±Visit Window)		-60 to -1	Day 1	15 (±3)	29 (±4)	57 (±4)	85 (±4)	113 (±4)	141 (±4)	169 (±7)	197 (±4)	225 (±4)	253 (±4)
Informed consent (and assent, if applicable)	If during the study the patient reaches the legal age for consent, the patient needs to consent before any study procedures can be performed	X											
Demographics		X											
Medical history	See Section 6.1.	X	X										
Inclusion/exclusion criteria		X											

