- Visits and study drug dosing may be conducted offsite where applicable country and local regulations and infrastructure allow (at the discretion of the Investigator, based on safety and tolerability), provided the patient has tolerated a dose of lumasiran administered in the clinic. If a visit is conducted offsite, a body system assessment may be performed in lieu of a physical examination.
- In situations where a study visit is unable to be completed (either at the site or offsite by a healthcare professional), the Investigator (or delegate) will verbally contact the patient within the study visit window to assess concomitant medications, renal stone events, adverse events, and healthcare utilization.
- See Section 4.3.1 for instructions for patients who discontinue study drug.
- Gray-shaded column indicate visits where assessments span 2 days.

Table 2: Schedule of Assessments – Open Label Extension Period (After Month 9 through Year 5)

Study Period	Study Visit	Open-Label Extension Period							Safety Follow-up (Patients who Discontinue Treatment)		
		Through Year 2				Through Year 5					
		M12	M15	M18	M21	M24	M27	M30; M36; M42; M48; M54	EOT M57	EOS/ ET M60	
Study Day (±Visit Window)	Note	337 (±28)	421 (±28)	505 (±28)	589 (±28)	673 (±28)	757 (±28)	Every 168 days (±28)	1597 (±28)	1681 (±28)	Every 84 days (±28)
Informed consent (and assent, if applicable)	If during the study the patient reaches the legal age for consent, the patient needs to consent before any study procedures can be performed										
Full physical examination	See Section 6.5.3.	X		X		X		X		X	
Symptom-directed physical examination	See Section 6.5.3.		X		X						X
Height	In triplicate for pediatric patients. See Section 6.5.2.	X		X		X		X		X	X
Body weight	See Section 6.5.2.	X	X	X	X	X		X		X	X
Vital signs	See Section 6.5.1.	X	X	X	X	X		X		X	X
12-lead electrocardiogram	See Section 6.5.4 and Table 3. For East Asian sites, see Table 4.	X				X		X (M36 and M48 only)		X	
Pregnancy test (WOCBP)	May be performed more frequently where required per local requirements, or if pregnancy is suspected. See Section 6.5.6.2.	X	X	X	X	X	X	X (every 84 days predose)	X	X	X
Clinical laboratory assessments	See Section 6.5.6.	X	X	X	X	X		X		X	X

Study Period	Open-Label Extension Period									Safety Follow-up (Patients who Discontinue Treatment)	
	Through Year 2						Through Year 5				
Study Visit	M12	M15	M18	M21	M24	M27	M30; M36; M42; M48; M54	EOT M57	EOS/ ET M60		

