3.6. Blinding

All site personnel (with the exception of some site pharmacists) and patients (including their families or caregivers) will be blinded to study drug treatment assignment until the last patient completes the assessments at the Month 9 visit. Site pharmacists may be unblinded to study drug treatment only where required by documented pharmacy procedure. All Sponsor personnel with direct oversight of the conduct and management of the study (except for staff involved in randomization and study drug supply) will be blinded to study drug treatment until the 6-month

treatment period data is unblinded for the primary analysis. Sponsor personnel who may have treatment assignment information will not have access to patient level data from the clinical trial databases.

The independent DMC and an independent biostatistics group will have access to patient level treatment assignments.

To maintain the blind to treatment assignment, during the 3-month blinded treatment extension period, study drug will continue to be administered in a double-blind manner and at the same frequency as in the 6-month double-blind period. However, the study is designed so that all patients will receive active drug during the extension period according to initial treatment assignment as follows:

- Patients randomized to placebo: 3.0 mg/kg lumasiran administered as monthly loading doses (Month 6, 7, and 8)
- Patients randomized to lumasiran: 3.0 mg/kg lumasiran administered as a single maintenance dose at Month 6

Therefore, all site personnel and patients will be aware that all patients will receive active drug administered at Month 6 even though all doses of study drug will be masked.

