From Month 12 through the end of the study, study drug administration may be conducted at a location other than the study center (eg, home) by a healthcare professional with the oversight of the Investigator, where applicable country and local regulations and infrastructure allow. However, continued study drug administration at the study center should be considered for patients who have ongoing study drug-related AEs, worsening injection site reactions with repeat dosing, or for anyone in the opinion of the Investigator who would benefit from clinical observation following dosing.

If the patient is unable to come to the study site, and a visit by a healthcare professional is not possible due to circumstances related to the COVID-19 pandemic, lumasiran may be administered by the patient or caregiver under the oversight of the Investigator, and following consultation with the Medical Monitor, as allowed by applicable country and local regulations. In such cases, the patient or caregiver must receive appropriate training on lumasiran administration prior to dosing. This measure is intended to remain in effect only during periods of time when the COVID-19 pandemic impedes the ability of patients to travel to the study site and healthcare professionals to go to patients' homes for dosing.

If a patient does not receive a dose of study drug within the specified dosing window, the Investigator should contact the Medical Monitor. After such consultation, the dose may be administered or considered missed and not administered.

If a patient misses multiple doses of study drug, the Investigator, in consultation with the Medical Monitor, will discuss whether the patient will be able to continue the study (see also Section 4.3).

Additional details can be found in the Pharmacy Manual. In addition, instructions and procedures related to administration of lumasiran by a patient or caregiver will be provided in the Patient/Caregiver Storage and Administration Instructions.

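### Protocol Table 1 allows offsite dosing before the Month 12 start given in Section 5.2.2, on a condition that blinded staff cannot verify through the Month 6 dose

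*Protocol*

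**What the plan says.** Four parts of the protocol bear on where a dose may be given before Month 12.

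- **Table 1, Notes.** The table covers both blinded periods, from screening to the Month 9 assessments. The note reads "Visits and study drug dosing may be conducted offsite where applicable country and local regulations and infrastructure allow", at the Investigator's discretion and "provided the patient has tolerated a dose of lumasiran administered in the clinic". It gives no start month, and the drug it names is lumasiran, not study drug.
- **Section 5.2.2, Dose and Administration.** "From Month 12 through the end of the study, study drug administration may be conducted at a location other than the study center", by a healthcare professional under the Investigator's oversight. A further paragraph deals with the pandemic: "lumasiran may be administered by the patient or caregiver under the oversight of the Investigator". It is limited by circumstance and not by study month: "This measure is intended to remain in effect only during periods of time when the COVID-19 pandemic impedes".
- **Section 3.1, Summary of Study Design.** Efficacy and safety assessments through Month 9 take place at visits to the clinical study center.
- **Section 3.6, Blinding.** Site personnel and patients "will be blinded to study drug treatment assignment until the last patient completes the assessments at the Month 9 visit". The one standing exception is narrow: "Site pharmacists may be unblinded to study drug treatment only where required by documented pharmacy procedure". The same section says that sites and patients will know that everyone receives active drug at Month 6.

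Sections 3.1 and 3.6 put the placebo arm's first lumasiran dose at Month 6.

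**The concern.** There are two problems, and they are separable.

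The first is a plain conflict. The study drug row of Table 1 refers the reader to Section 5.2.2, so a site planning a dose meets both rules. A Month 12 start for healthcare-professional dosing has little purpose if the same dosing was already allowed from Month 1.

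The second is the condition. In the placebo-controlled period the Investigator who holds the discretion does not know who has received lumasiran. If the condition is taken literally, only lumasiran patients can be cleared, so the place of dosing discloses the arm. If it is taken loosely, as any tolerated injection, a patient who has had only saline satisfies it. The assurance that the note seeks is then absent at the one dose where it counts most for that patient.

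**Working it through.** No figure in the plan bears on this, so the check is a comparison of passages and a count by hand.

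**Dosing visits in Table 1.** Day 1 and Months 1, 2, 3, 6, 7, 8 and 9. Day 1 has no earlier dose, so the condition cannot be met there. That leaves 8 − 1 = 7 visits.

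**Conflict with Section 5.2.2.** All seven come before Month 12. At each, the note allows offsite dosing if its condition holds, while the Month 12 provision has not yet begun. The COVID-19 paragraph does not close the gap. It covers dosing by the patient or caregiver, in pandemic circumstances, whereas the note has no pandemic limit and no such restriction on who gives the dose. Section 6 allows many assessments offsite at all timepoints, but dosing is not in its list. Section 3.1 is weaker support, because it speaks of assessment visits and Section 6 relaxes that. The main conflict is with Section 5.2.2.

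**Can a blinded Investigator verify the condition?**

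| Dose | Earlier doses, lumasiran arm | Earlier doses, placebo arm | Verifiable under the blind? |
|---|---|---|---|
| Months 1, 2, 3 | lumasiran | placebo only | No |
| Month 6 | lumasiran | placebo only | No |
| Months 7, 8, 9 | include lumasiran at Month 6 | include lumasiran at Month 6 | Yes, if the Month 6 dose was given in the clinic and tolerated |

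So 4 of the 7 visits are unverifiable and 3 are verifiable. Month 9 is the first open-label dose. Of the six blinded dosing visits after Day 1, 4 are unverifiable and 2 (Months 7 and 8) are verifiable.

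**Patients who cannot meet the condition at those four visits.** With 30 planned patients randomized 2:1, the placebo arm is 30 × 1/3 = 10.

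**Where the loose reading bears on safety.** At Months 1 to 3 a placebo patient dosed offsite receives saline, and a lumasiran patient dosed as scheduled has had lumasiran since Day 1. A first active dose given offsite can arise only at Month 6, in the placebo arm.

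**The case against.** The best reply is that the note is permissive. It says that dosing may be offsite if a condition holds. If a blinded Investigator cannot confirm the condition, the permission is not triggered and the dose stays in the clinic. Nothing tells a site to break the code, and Section 3.6.1 reserves that for clinical management that requires knowing the assignment. This is a fair reading, and it means that the note does not compel unblinding. It does not make the note sound: a permission that no blinded person can use correctly at four visits should not stand in the schedule for those visits.

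Month 6 is also a visit poorly suited to offsite dosing. It calls for vital signs 30 minutes after the dose, triplicate ECGs on a central machine before and 4 hours after the dose, and a renal ultrasound. Neither the ECG nor the ultrasound is in Section 6's offsite list, and the COVID-19 deferrals for both apply only at Month 12 and later. This makes an offsite Month 6 dose unlikely. The note still does not exclude it, and the Section 6 list is worded as examples.

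Two stronger readings are tempting. A reader might infer that the condition fails throughout both blinded periods. It does not, because everyone is known to receive lumasiran at Month 6. A reader might also infer that Section 5.2.2 confines all offsite dosing to Month 12 onward. It does not: the Month 12 sentence is not worded as exclusive, and the COVID-19 route has no month limit.

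**Conclusion.** The point holds as an internal inconsistency together with a condition that cannot be applied as worded for part of the trial. The passages differ on routine offsite dosing by a healthcare professional at seven visits, Month 1 through Month 9. At four of them, Months 1, 2, 3 and 6, the condition cannot be verified under the blind. The safety consequence is confined mainly to the Month 6 dose in the placebo arm, about 10 patients if the 2:1 split is exact.

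That 10 is the size of an arm, not an estimate of harm. The documents do not give the number of offsite doses, or of patients still before Month 6 when this wording applied. A reader might infer that the primary result is at risk. The documents do not support that: the endpoint is a centrally analyzed laboratory value, and no analysis or error rate is shown to be affected. It should be corrected because two operative rules disagree on where blinded doses may be given, and one of them, followed to the letter before the Month 6 dose, would disclose the assignment.

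The matching note under Table 2 raises no blinding problem, since dosing there is open-label.

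**What to change.** Reconcile the Table 1 note with Sections 3.1 and 5.2.2 so that all three state the same rule on when routine offsite dosing may begin, and say how the COVID-19 provision relates to it. For visits through Month 6, reword the condition so that a blinded Investigator can judge it without knowing the assignment. Substituting a blinded term for the drug's name would remove the blinding problem, but it would also settle what assurance is required before the placebo arm's first lumasiran dose. That choice, like the start month, is clinical and is for the sponsor to make and state openly.

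The cost is a wording change in one table note and the matching sections. It affects no data, sample size or analysis.

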AUC	Area under the concentration-time curve
BSA	Body surface area
C _{max}	Maximum plasma concentration
CFR	Code of Federal Regulation
CL/F	Apparent clearance
COVID-19	Coronavirus disease 2019
DMC	Data Monitoring Committee
ECG	Electrocardiogram
eCRF	Electronic case report form
eGFR	Estimated glomerular filtration rate
EOS	End of study
EOT	End of treatment
ET	Early termination
EQ-5D	Euro Quality of Life Health State Profile Questionnaire
ESRD	End-stage renal disease
FAS	Full analysis set
GalNAc	N-acetylgalactosamine
GCP	Good Clinical Practice
GLP	Good Laboratory Practice
GO	Glycolate oxidase
HAO1	Hydroxyacid oxidase 1
HBV	Hepatitis B virus
HCV	Hepatitis C virus
HIV	Human immunodeficiency virus

Abbreviation	Definition
ICF	Informed consent form
ICH	International Council on Harmonisation
IEC	Independent Ethics Committee
IND	Investigational New Drug
INR	International normalized ratio
IRB	Institutional Review Board
IRS	Interactive Response System
ISR	Injection site reactions
KDQOL	Kidney Disease Quality of Life Questionnaire
LFT	Liver function tests
MAD	Multiple-ascending dose
MDRD	Modification of diet in renal disease
MedDRA	Medical Dictionary for Regulatory Activities
MMRM	Mixed-effect model for repeated measures
MNAR	Missing not at random
mRNA	Messenger ribonucleic acid
OLE	Open-label extension
PD	Pharmacodynamic
PedsQL	Pediatric Quality of Life Inventory
PH1	Primary hyperoxaluria type 1
PK	Pharmacokinetic
PMM	Pattern mixture model
PP	Per protocol
PT	Preferred Term
q3M	Once every 3 months
qM	Once monthly
qMx3	Once monthly for 3 consecutive months
SAD	Single-ascending dose
SAE	Serious adverse event
SAP	Statistical analysis plan
SC	Subcutaneous
siRNA	Small interfering RNA

Abbreviation	Definition
SOC	System Organ Class
SUSAR	Suspected unexpected serious adverse reaction
$t_{1/2\beta}$	Elimination half-life
t_{max}	Time to maximum plasma concentration
TMF	Trial master file
ULN	Upper limit of normal
V/F	Apparent volume of distribution
VAS	Visual analog scale
WOCBP	Women of child-bearing potential
WHO	World Health Organization

1. INTRODUCTION

1.1. Disease Overview

Primary hyperoxaluria type 1 (PH1) is a rare autosomal recessive disease characterized by excessive oxalate production by the liver and consequent hyperoxaluria. PH1 is caused by mutations in the alanine glyoxylate aminotransferase (*AGXT*) gene, which encodes the liver peroxisomal enzyme alanine-glyoxylate aminotransferase (AGT). As a consequence of AGT deficiency, glyoxylate accumulates and is oxidized to oxalate in the hepatocyte and ultimately transported to the kidneys for excretion. Oxalate, in the form of its calcium salt, is excreted almost entirely by the kidney. Due to its insolubility, calcium oxalate can crystallize readily in the urinary tract. In PH1, excess urinary oxalate results in recurrent nephrolithiasis and/or nephrocalcinosis, which can lead to pain, infections, progressive kidney disease and failure, along with reduced quality of life.[\[Cochat and Rumsby 2013\]](#) As renal function declines, elimination of oxalate is further reduced, such that calcium oxalate accumulates in bone, vasculature, skin, retina, heart, and nervous system, resulting in severe end-organ damage.[\[Cochat and Rumsby 2013\]](#) This devastating condition, systemic oxalosis, arises when the estimated glomerular filtration rate (eGFR) has declined to below 30 to 45 mL/min/1.73 m².[\[Cochat and Rumsby 2013\]](#) Without treatment, the disease progresses inexorably, and death from end-stage renal disease (ESRD) and/or complications of oxalosis is inevitable.[\[Cochat and Rumsby 2013; Harambat 2010; van der Hoeven 2012\]](#)

Over 150 mutations in *AGXT* have been described.[\[Williams 2009\]](#) While there are broad genotype–phenotype associations with the underlying causative defect, patients can present with very different symptoms, disease course, including timing of an individual’s eGFR decline, and treatment response.[\[Danpure 2014; Hoppe 1997\]](#) Patients progress at various rates and an event that leads to acute or chronic worsening, such as an obstructive kidney stone or episode of dehydration, can occur at any time.

The incidence of PH1 is approximately 1 in 120,000 live births, and the prevalence is 1 to 3 per million in North America and Europe.[\[Cochat and Rumsby 2013; Hopp 2015; Hoppe 2010\]](#) The disease is more prevalent in areas where consanguineous marriages are common, especially in the Middle East and Northern Africa.[\[Al-Eisa 2004; Boualla 2015; Frishberg 2005; Kamoun and Lakhoua 1996\]](#)

PH1 often presents as a pediatric disease, but many patients remain undiagnosed for years after the initial clinical manifestations of the disease.[\[Lieske 2005; Mandrile 2014; van Woerden 2003\]](#) A recently published analysis of 247 patients with PH1 from 206 pedigrees in the Rare Kidney Stone Consortium PH Registry demonstrated a median age of first symptoms at 5.2 years of age and a cumulative renal survival of 76%, 43%, and 12% at 20 years, 40 years, and 60 years, respectively.[\[Hopp 2015\]](#) Similarly, an analysis of 526 patients with PH1 published by the OxalEurope Consortium indicated a median age of disease symptom onset of 3.9 years and a median age of diagnosis of 8.1 years. Overall, 43% of all patients diagnosed with PH1 had already progressed to ESRD at the time of diagnosis.[\[Mandrile 2014\]](#) The deterioration of renal function highlights the importance of investigating potentially disease-modifying interventions as soon as possible after diagnosis.

There are no approved therapies for the treatment of PH1 and the current standard of care is burdensome to patients and their families. Disease management is based on supportive measures, including high fluid intake and crystallization inhibitors to increase urinary oxalate solubility, and treatment of disease complications such as urinary tract stones and infections. A minority of patients experience oxalate lowering with therapeutic doses of pyridoxine (vitamin B6). Dietary modification plays a minor role in treatment since endogenous oxalate production far exceeds dietary intake. Patients progressing to, or presenting with ESRD require intense kidney dialysis. Dialysis is not viewed as an effective therapy for PH1, but rather serves as a bridge to a liver-kidney transplant or as an alternative to no therapy at all. Dialysis is often inadequate to effectively offload accumulating oxalate, and systemic oxalosis with end organ damage may develop despite this burdensome treatment. Dialysis regimens for PH1 are more involved than conventional dialysis, predisposing to increased risk of complications. Combined liver/kidney transplantation offers potentially curative therapy; but is limited due to restricted availability, complications associated with the procedure, ethical considerations in resource-poor settings [[Cochat and Rumsby 2013](#)], and intense use of health care resources.

PH1 can progress to be a serious, severely debilitating disease with significant morbidity and mortality and negatively impacts quality of life. Limited and burdensome management options for PH1 outlined above highlight the serious unmet need for a safe and efficacious treatment for patients with this devastating disease.

